2.1. Study Rationale

LY3041658 is a humanized immunoglobulin G (IgG) 4-variant monoclonal antibody (mAb) that binds to and neutralizes all 7 of the known ligands (referred to collectively as ELR+ [E = glutamic acid, L = leucine, R = arginine] chemokines) that signal through the human chemokine, CXC motif, receptors 1 and 2 (CXCR1 and CXCR2). LY3041658 binds to an epitope that is common to all 7 ELR+ chemokines. Signaling through CXCR1 and CXCR2 modulates neutrophil migration and angiogenesis, and neutrophil migration into sites of inflammation is critical to the pathogenesis of hidradenitis suppurativa (HS). Thus, LY3041658 is being developed for the treatment of HS.

Study I7P-MC-DSAD (DSAD) is a Phase 2 study to evaluate the safety and efficacy of LY3041658 in adult patients with HS. Results of this study will provide information useful to guiding dose selection in future studies and to further characterize the benefit/risk profile of LY3041658.

2.2. Background

Hidradenitis suppurativa (HS) or acne inversa is a chronic, recurrent, inflammatory, debilitating skin disease usually presenting after puberty with painful, deep, inflamed lesions in the apocrine gland-bearing areas of the body, commonly the inguinal axillaries, and anogenital regions (Zouboulis et al. 2015; Zouboulis 2006).

Even when HS lesions heal, permanent fibrosis, dermal contractures, and induration of the skin frequently occur. These tissue changes can be physically, psychologically, and cosmetically debilitating. As tissue damage accumulates over time, patients frequently develop low self-esteem and loneliness (Kouris et al. 2016) and become socially withdrawn, unable to maintain employment, and susceptible to poverty, depression, and suicidality (Vekic and Cains 2017).

There is currently no uniformly effective single therapy for HS. Numerous treatment modalities are employed, including antibiotics, retinoids, hormones, immunosuppressive and anti-inflammatory agents, neurotoxins, radiotherapy, and surgery. The tumor necrosis factor inhibitor adalimumab has been approved in the United States, Europe, and Australia for the treatment of moderate-to-severe HS (Zouboulis et al. 2015; Kimball et al. 2016a; Vekic and Cains 2017). Yet substantial unmet medical needs remain, since adalimumab fails either to treat many patients adequately or to maintain treatment effect over time (Kimball et al. 2016a). Patients with HS are appropriate for a novel investigational product (IP) with immunomodulating properties.

2.3. Benefit/Risk Assessment

The efficacy of LY3041658 in HS has not been established. However, LY3041658 decreased neutrophil migration into cantharidin-induced blisters in healthy participants (data on file, Study I7P-MC-DSAA [DSAA]). These findings support the hypothesis that LY3041658 has the

potential for efficacy in HS and other neutrophilic skin diseases. Furthermore, participants may benefit by receiving personal health information from the physical examinations and from other routine safety assessments performed in this study.

At this time, there are no known adverse drug reactions (ADRs) or known risks considered to be associated with LY3041658. No dose-limiting events were observed in the Phase 1 studies DSAA and I7P-MC-DSAB [DSAB].

In the Phase 1 Study DSAA, single doses of up to 700 mg of LY3041658 administered to healthy study participants were generally well tolerated with the exception of a mild, short-lived, infusion-associated reaction in 1 participant in a 700-mg cohort.

In the Phase 1 Study DSAB, participants with psoriasis, HS, or palmoplantar pustulosis received 40 mg to 600 mg doses of LY3041658 every 2 weeks. The most common treatment-emergent adverse events were infections such as cellulitis, sinusitis and respiratory tract infections. Most adverse events were mild to moderate (CTCAE Grade 1 or Grade 2) severity. There was one severe event of elevated gamma-glutamyl transferase (GGT) (CTCAE Grade 3); this event in a single participant assigned to LY3041658 300 mg, and it was not accompanied by symptoms or changes in aspartate aminotransferase (AST) or alanine aminotransferase (ALT) greater than 3 times the upper limit of normal (ULN).

To minimize participant risk in Study DSAD, all participants will be monitored closely after completion of each intravenous (IV) infusion (Section 6.1). In addition, all participants will undergo regular monitoring of routine laboratory safety tests (clinical chemistry, hematology, and urinalysis). Monitoring of safety data will be performed on an ongoing basis, as described in Section 8.2. Interim analyses to review unblinded safety data will also be conducted, as described in Section 9.5 and Appendix 10.1, Section 10.1.5.

In summary, in the context of the cumulative knowledge for LY3041658, the benefit/risk balance for this study is assessed to be favorable.

More detailed information about the known and expected benefits and risks and reasonably expected adverse events of LY3041658 may be found in the Investigator's Brochure (IB).

3. Objectives and Endpoints

Endpoints					
Proportion of participants achieving HiSCR response at Week 16					
 Mean change from baseline to Week 16 in: Total number of abscesses and inflammatory nodules (AN count) Skin Pain – HS Numeric Rating Scale (NRS) 					

Exploratory

Exploratory objectives and endpoints may include the following:

- To evaluate, at various time points, the efficacy of LY3041658 compared to placebo in inducing improvements in signs and symptoms and quality of life
- To characterize the pharmacokinetics (PK) of LY3041658 and to explore relationships between LY3041658 exposure and select biomarkers and clinical efficacy endpoints
- To assess the potential development of anti-LY3041658 antibodies and their impact on the safety profile and PK of LY3041658

Note: HiSCR is defined as at least a 50% reduction in the total abscess and inflammatory nodule count (AN count) with no increase in abscess count and no increase in draining fistulae count relative to baseline.

4. Study Design

4.1. Overall Design

Study I7P-MC-DSAD (DSAD) is a multicenter, randomized, double-blind, placebo-controlled, parallel-group Phase 2 study to evaluate the efficacy and safety of LY3041658 600 mg given intravenously (IV) every 2 weeks (Q2W) in adults with HS.

The study duration will be up to approximately 51 weeks over 4 study periods:

Screening: a period lasting up to 35 days before Week 0 (Visit 2, baseline)

Treatment Period 1: a 16-week, 2-group double-blind treatment period:

• At baseline (Visit 2, Week 0), eligible participants will be randomized in a 2:1 ratio to receive either LY3041658 600 mg IV Q2W or placebo IV Q2W, starting at the baseline visit.

Treatment Period 2: a 20-week, single-group open-label extension period:

• Starting at Week 16, all participants, including those previously assigned to placebo, will receive LY3041658 600 mg IV Q2W until the last dosing visit.

Post-treatment follow-up: a period lasting approximately 10 weeks.

- Participants will not receive study drug in this period.
- The last dose of study drug is given at Visit 19 (Week 34). Thus, participants will have been withdrawn from study drug for a total of 12 weeks at the last post-treatment follow-up visit (Visit 802, Week 46).

The study schema is presented in Section 1.2.

Unscheduled visits are for participants needing rescue therapy or incision and drainage. The use of concomitant medications, including rescue therapy, is described in Section 6.5.

Participants who permanently discontinue the study drug early (Section 7.1) will undergo early termination procedures, including an early termination visit (ETV) and the post-treatment follow-up visits specified in the Schedule of Activities (SoA) (Section 1.3).

4.2. Scientific Rationale for Study Design

The primary endpoint of this study is the proportion of patients achieving Hidradenitis Suppurativa Clinical Response (HiSCR) at Week 16. HiSCR is defined as at least a 50% reduction in the total abscess and inflammatory nodule count (AN count) with no increase in abscess count and no increase in draining fistulae count relative to baseline. HiSCR has been used in previous HS trials and has been accepted by the Food and Drug Administration as a primary endpoint (Kimball et al. 2014; Kimball et al. 2016a; Kimball et al. 2016b). Evaluation of the primary endpoint at the Week 16 time point is appropriate based on current clinical trials of systemic immunomodulatory therapies in HS (guselkumab NCT03628924, secukinumab NCT03713632 and NCT03713619; bimekizumab NCT04242498 and NCT04242446).

A double-blind, placebo-controlled design through the first treatment period limits bias for the participant and investigator assessments and enables a clearer interpretation of the effects of active drug.

The second treatment period (open-label) allows for evaluation of both safety and changes in efficacy over time in participants who received LY3041658 in the placebo-controlled treatment period. The second treatment period also allows participants who were randomized to placebo in the first treatment period to receive LY3041658 in the open-label period for a treatment duration similar to that of the placebo-controlled period.

The post-treatment follow-up period allows for continued safety monitoring after the last dose. The last dose is given at Week 34. This is 2 weeks before the last visit in the second treatment period (Week 36) and a total of 12 weeks before the last post-treatment follow-up visit (Week 46). LY3041658 concentrations are expected to be significantly decreased in the plasma after 5 half-lives. The terminal half-life of LY3041658 is approximately 2 weeks, based on pharmacokinetic (PK) data from the Phase 1 Study DSAB. Therefore, for the present study, the planned duration of safety follow-up is adequate, as this duration covers approximately 6 half-lives. A follow-up period of a similar duration was used after the last dose of LY3041658 in the single-dose Study DSAA and multiple-dose Study DSAB.

4.2.1. Participant Input into Design

The sponsor involved patients in the design of this study by engaging patients in simulations and other face-to-face or virtual collaborative events for related HS trials. The insights gained from these events were used to ensure that this study design is supportive of the well-being of the study participants and that the study procedures can be implemented effectively at the investigative sites.

4.3. Justification for Dose

The dose of 600 mg IV Q2W matches the highest dose administered in the multiple-dose Study DSAB. The Q2W dosing frequency was selected because the LY3041658 terminal half-life is approximately 2 weeks. In Study DSAB, three participants with HS received 4 doses of LY3041658 Q2W. There were no deaths, serious adverse events, or treatment-emergent adverse events leading to discontinuation in Study DSAB.

Exploratory modeling of neutrophil migration into cantharidin-induced blisters in healthy participants (Study DSAA) was performed. Although the neutrophil data was highly variable, a trend of dose-dependent decreases of neutrophils in the blister fluid was observed. Based on simulations using the exploratory PK/PD model, a 600 mg IV Q2W dose was predicted to reduce neutrophil migration to <20% of the baseline value.

The margin of safety (MOS) calculation is summarized in the IB. The estimated AUC(0-168) exposure based on three HS participants at the clinical IV dose of 600 mg (71500 μ g*hr/mL) in humans is 7.2-fold lower than the AUC(0-168) at the NOAEL (125 mg/kg IV) in cynomolgus monkeys administered LY3041658 once weekly for 6 months.

See the IB for additional information.

4.4. End-of-Study Definition

A participant is considered to have completed the study if he or she has completed all required phases of the study, including the last visit or the last scheduled procedure shown in the SoA (Section 1.3).

The "end of the study" is defined as the date of the last visit or last scheduled procedure shown in the SoA for the last participant in the study globally.

5. Study Population

Prospective approval of protocol deviations to recruitment and enrollment criteria, also known as protocol waivers or exemptions, is not permitted.

All screening evaluations must be completed and reviewed to confirm that potential participants meet all eligibility criteria.

The investigator will maintain a screening log to record details of all participants screened and to confirm eligibility or record reasons for screening failure, as applicable.

For screen failures and rescreening activities within the screening period, see Section 5.4.

5.1. Inclusion Criteria

Participants are eligible to be included in the study only if they meet all of the following criteria during the screening period, unless otherwise specified below:

Informed consent

[1] Are capable of giving signed informed consent as described in Appendix 10.1, which includes compliance with the requirements and restrictions listed in the informed consent form (ICF) and in this protocol.

Participant characteristics

[2] Are male or female patients from 18 to 65 years of age (inclusive), at the time of signing the ICF.

Note: Contraceptive use by men or women should be consistent with local regulations regarding the methods of contraception for those participating in clinical studies. Contraception requirements for participants in this study are provided in Appendix 10.4.

HS-related inclusion criteria

- [3] Have a diagnosis of HS for at least 6 months before baseline (the randomization visit).

 Note: a participant with a clinical history of HS may be considered for enrollment if other eligibility criteria are met and if the clinical history is documented by the investigator based on review of the participant's medical history at screening.
- [4] Have HS lesions in at least 2 distinct anatomical regions (for example, right and left axilla; or right axilla and right inguino-crural fold); and at least one of the lesions must be at least Hurley Stage II or Hurley Stage III.
- [5] Have had an inadequate response or intolerance to a 28-day course of oral antibiotics. Examples of inadequate response include the following: any lesion increased in Hurley stage, any lesion requiring intra-lesional steroid injection or incision and drainage, and/or any new anatomic areas developed lesions during the antibiotic course.
- [6] Have a total abscess and inflammatory nodule (AN) count greater than or equal to 4.
- [7] Must agree to use daily, and throughout the duration of the study, one of the following over-the-counter topical antiseptics on body areas affected with HS lesions: chlorhexidine gluconate, triclosan, benzoyl peroxide, or dilute bleach in water.

[8] Are able and willing to comply with the following requirements for use of antibiotics:

If using topical antibiotics for HS at screening, the participant must stop them at least 14 days before baseline (the randomization visit) and must not resume topical antibiotics throughout the duration of the study.

If using oral antibiotics for HS at screening and intends to continue them during the study, the participant must have been on a stable dose for at least 4 weeks before screening and must remain on the same stable dose throughout the duration of the study.

If using oral antibiotics for HS at screening and intends not to take them during the study, the participant must have stopped using them at least 14 days before the planned randomization visit (see Section 6.5).

Note: Participants may be considered for enrollment if they have received oral antibiotics for HS prior to screening but have stopped that use at least 14 days before the planned randomization visit.

5.2. Exclusion Criteria

Participants will be excluded from study enrollment if they meet any of the following criteria within the screening period, unless otherwise specified:

Skin diseases and conditions

- [9] Have more than 20 draining fistulae.
- [10] Have had surgical treatment for HS in the last 4 weeks prior to baseline (the randomization visit).
- [11] Have active skin disease or condition (for example, bacterial, fungal or viral infection) that could interfere with assessment of HS.

Prior or concomitant therapy

- [12] Are unwilling or unable to stop treatment with topical antibiotics for HS 14 days prior to baseline (the randomization visit) and for the duration of the study.
- [13] Have received any biologic agent for treatment of HS (for example, adalimumab) at any time.
- [14] Have received any biologic agent (such as monoclonal antibodies, whether investigational or marketed) for any indication other than HS within 3 months or 5 half-lives (whichever is longer) before baseline (the randomization visit).
 - Note: Participants may be considered for enrollment if they have stopped receiving a biologic agent for an indication other than HS at least 3 months or 5 half-lives (whichever is longer) before baseline (the randomization visit) and if all other eligibility criteria are met.
- [15] Have received any systemic nonbiologic immunosuppressive medication for any indication within 28 days before baseline (the randomization visit).

[16] Have received oral opioids for HS-related pain within 14 days before baseline (the randomization visit) or are anticipated to receive oral opioids for HS-related pain during the study.

- Note: Participants may be considered for enrollment if they have stopped receiving oral opioids for HS-related pain more than 14 days before the baseline visit and if all other eligibility criteria are met.
- [17] Have received any systemic (including oral) antibiotic or anti-infective treatment within 28 days prior to baseline (the randomization visit), unless as required for latent tuberculosis infection (LTBI) treatment (see criterion #25) or prescribed for HS (see criterion #8).
- [18] Have a history of chronic alcohol abuse, IV drug abuse, or other illicit drug abuse within 1 year prior to the screening visit.
 - Note: Marijuana is considered an illicit drug for the purposes of this study, regardless of local laws. Cannabidiol (CBD) products may be used during the study if they are derived exclusively from hemp. Participants who use hemp-based CBD products must be on a stable dose for at least 14 days prior to baseline (the randomization visit), and participants must remain on that stable dose during the study.

Current or historical infections

- [19] Have a current or recent acute, active infection. For at least 30 days prior to screening and up to the randomization visit, participants must have no symptoms or signs of confirmed or suspected infection, and must have completed any appropriate anti-infective treatment.
 - Note: Participants with an active upper respiratory infection that is being treated only symptomatically and does not require anti-infectives may be considered for enrollment if other eligibility criteria are met.
- [20] Have had, within 12 weeks of screening and up to the randomization visit, any of the following types of infection
 - Serious (requiring hospitalization, and/or IV or equivalent oral antibiotic treatment)
 - Opportunistic (as defined in Winthrop at al. 2015; see Appendix 10.6).
 Note: Herpes zoster is considered active and ongoing until all vesicles are dry and crusted over.
 - Chronic (duration of symptoms, signs, and/or treatment of 6 weeks or longer)
 - Recurring (including, but not limited to, herpes simplex, herpes zoster, recurring cellulitis, chronic osteomyelitis).
 - Note: Participants with only recurrent, mild and uncomplicated orolabial and/or genital herpes may be discussed with the sponsor's designated medical monitor and may be considered for enrollment if other eligibility criteria are met.
- [21] Have human immunodeficiency virus (HIV) infection
- [22] Have a current or past infection with hepatitis B virus (HBV) (that is, positive for hepatitis B surface antigen [HBsAg] and/or hepatitis B core antibody) (see Section 8.2.7).

[23] Have a current infection with hepatitis C virus (that is, positive for HCV ribonucleic acid [RNA]).

- [24] Have current or past history of active tuberculosis (TB) (see Section 8.2.6).
- [25] Have or have had LTBI that has not been treated with a complete course of appropriate therapy as defined by the World Health Organization and/or the United States Centers for Disease Control and Prevention, unless such treatment is underway (see Section 8.2.6).

Vaccines

[26] Have received a Bacillus Calmette-Guerin (BCG) vaccination or treatment within 12 months before screening; or received any live vaccine (that is, live attenuated) within 3 months before screening, or intend to receive a live vaccine (or live attenuated) during the study. Note: Use of nonlive (inactivated) vaccinations is allowed for all participants.

Other medical conditions or history

- [27] Have a diagnosis or history of malignant disease within 5 years before baseline (the randomization visit), with the following exceptions:
 - o basal cell or squamous epithelial carcinomas of the skin that have been resected with no evidence of metastatic disease for 3 years
 - o cervical carcinoma in situ, with no evidence of recurrence within the 5 years prior to baseline.
- [28] Have answered "yes" to either Question 4 or Question 5 on the "Suicidal Ideation" portion of the Columbia-Suicide Severity Rating Scale (C-SSRS) or
 - have answered "yes" to any of the suicide-related behaviors on the "suicidal behavior" portion of the C-SSRS,
 - and the ideation or behavior occurred within 4 weeks prior to screening and up to the randomization visit.
- [29] Are, in the judgment of the investigator, actively suicidal and therefore deemed to be at significant risk for suicide.
- [30] Have significant history of or current cardiovascular, respiratory, hepatic, renal, gastrointestinal, endocrine, hematological, or neurological disorders capable of significantly altering the absorption, metabolism, or elimination of drugs; of constituting a risk when taking the IP; or of interfering with the interpretation of data.
- [31] Are immunocompromised.
- [32] Have clinically significant multiple or severe drug allergies, or intolerance to topical corticosteroids, or severe posttreatment hypersensitivity reactions (including, but not limited to, erythema multiforme major, linear immunoglobulin [Ig] A dermatosis, toxic epidermal necrolysis, or exfoliative dermatitis).
- [33] Have significant allergies to humanized monoclonal antibodies or any components of the LY3041658 product formulation.

Diagnostic assessments

[34] Have screening electrocardiogram (ECG) abnormalities that, in the opinion of the investigator, are clinically significant and indicate an unacceptable risk for the participant's safety in the study.

- [35] Have any of the following specific abnormalities on screening laboratory tests:
 - a. Creatinine ≥2 times ULN
 - b. AST or ALT ≥2 times ULN
 - c. Alkaline phosphatase (ALP) ≥2 times ULN
 - d. Total bilirubin level (TBL) ≥1.5 times ULN
 - e. Hemoglobin < 9.0 g/dL (< 90.0 g/L)
 - f. Total white blood cell (WBC) count $<2500 \text{ cells/}\mu\text{L}$ ($<2.50 \text{x} 10^3/\mu\text{L}$ or <2.50 GI/L)
 - g. Neutropenia (absolute neutrophil count <1200 cells/ μ L) (<1.20x10³/ μ L or <1.20 GI/L)
 - h. Lymphopenia (absolute lymphocyte count <750 cells/ μ L) (<0.75x10³/ μ L or <0.75 GI/L)
 - i. Thrombocytopenia (platelet count <100,000 cells/μL) (<100x10³/μL or <100 GI/L)

Note: For each aforementioned test, 1 repeat testing is allowed during screening, and values resulting from repeat testing may be accepted for a participant's enrollment eligibility if the other eligibility criteria are met (see Section 5.4.1).

Prior or concurrent clinical study experience

- [36] Have participated, within the last 30 days before baseline (the randomization visit), in a clinical trial involving any investigational product (IP). If the previous IP has a half-life of greater than 7 days, at least 3 months or 5 half-lives (whichever is longer) should have passed before enrollment in this study.
- [37] Have previously completed or withdrawn from this study or from any other study investigating LY3041658, and have previously received the IP.
- [38] Are currently enrolled in any other clinical study involving an IP or any other type of medical research judged not to be scientifically or medically compatible with this study.

Other exclusions

- [39] Are pregnant or breastfeeding, or intend to become pregnant or breastfeed during the study.
- [40] Have donated more than a single unit of blood within 4 weeks prior to the screening visit or intend to donate blood during the course of the study.
- [41] Have no contraindication to, and in the investigator's opinion are candidate for use of, at least one of the following: chlorhexidine gluconate, triclosan, benzoyl peroxide, or dilute bleach in water.

[42] Are investigative site personnel directly affiliated with this study and/or their immediate families. Immediate family is defined as a spouse, parent, child, or sibling, whether biological or legally adopted.

- [43] Are employees of Eli Lilly and Company (Lilly) or are employees of a third-party organization involved in the study which requires exclusion of their employees.
- [44] Are, in the opinion of the investigator or sponsor, unsuitable for inclusion in the study.

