Topical antiseptics will be required as concomitant therapy during the study. Participants who were on stable doses of oral antibiotics at screening will remain on the same stable dose throughout the study.

Disclosure Statement: In this study, the 2-arm parallel treatment period is participant-blinded and investigator-blinded and is followed by a single-arm open-label extension treatment period.

Number of Participants: Approximately 100 patients will be screened to achieve approximately 63 randomized participants.

Intervention Groups and Duration:

[figure not shown]
At baseline, participants will be randomized in a 2:1 ratio to one of two treatments groups:

Approximately 42 participants will receive LY3041658 600 mg IV Q2W for 16 weeks, and Approximately 21 participants will receive placebo IV Q2W for 16 weeks.

Starting at Week 16, all participants, including those previously assigned to placebo, will receive LY3041658 600 mg IV Q2W for 20 weeks.

Data Monitoring Committee: No

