7.2.1. Discontinuation of Inadvertently Enrolled Participants

If the sponsor or investigator identifies a participant who did not meet enrollment criteria and was inadvertently enrolled, then the participant should be discontinued from study treatment unless there are extenuating circumstances that make it medically necessary for the participant to continue on study treatment. If the investigator and the sponsor's clinical research physician agree that it is medically appropriate to continue, the investigator must obtain documented approval from the sponsor's clinical research physician to allow the inadvertently enrolled participant to continue in the study with or without treatment with investigational medicinal product. Safety follow-up is as outlined in the SoA (Section 1.3), Section 8.2 ("Safety Assessments), and Section 8.3 ("Adverse Events and Serious Adverse Events").

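### Exclusion criterion 41 is worded the wrong way round: it excludes people suited to a topical antiseptic that criterion 7 and Section 6.5.2 require them to use

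*Protocol*

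**What the plan says.** Protocol Section 5.2 opens with the rule that "Participants will be excluded from study enrollment if they meet any of the following criteria within the screening period, unless otherwise specified". Criterion 41 in that list reads: "Have no contraindication to, and in the investigator's opinion are candidate for use of, at least one of the following", followed by "chlorhexidine gluconate, triclosan, benzoyl peroxide, or dilute bleach in water". It carries no note that changes its sense.

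Protocol Section 5.1 opens with the opposite rule: "Participants are eligible to be included in the study only if they meet all of the following criteria during the screening period". Criterion 7 in that list says that participants "Must agree to use daily, and throughout the duration of the study, one of the following over-the-counter topical antiseptics", and then names the same four products. The synopsis states: "Topical antiseptics will be required as concomitant therapy during the study". Section 6.5.2 repeats the requirement and again names the four.

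Three other places bear on what follows if someone is enrolled against a criterion:

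- The opening of Protocol Section 5 says: "Prospective approval of protocol deviations to recruitment and enrollment criteria, also known as protocol waivers or exemptions, is not permitted". The opening of Section 8 repeats that waivers are not allowed.
- Protocol Section 7.2.1 says that, for an inadvertently enrolled person, "the participant should be discontinued from study treatment unless there are extenuating circumstances" that make continuing medically necessary. Continuing needs documented approval from the sponsor's physician.
- SAP Section 6.11 gives incorrect enrollment as one potential example of a deviation, and leaves its importance to review meetings and a separate document.

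**The concern.** An exclusion list should describe the people to be kept out. Criterion 41 describes the people whom the rest of the protocol needs: those able to use one of the required antiseptics. The sentence reads like an inclusion criterion placed in the wrong list, or like an exclusion criterion that has lost its negation.

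This is an operative eligibility rule. Sites confirm the criteria at Visits 1 and 2, and Section 5.4 requires eligibility details to be kept for screen failures. A site that follows the text exactly would turn away suitable people. A site that follows the evident intent enrolls people who, on paper, meet an exclusion criterion under a protocol that allows no waivers. The literal reading is also the one that admits people unsuited to a product that the protocol requires every day. The text therefore works against the purpose it appears to have.

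**Working it through.** No sample size, power or alpha figure is at issue, so the main check is one of logic.

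**Definitions**

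- A: the person agrees to use one of the four antiseptics (criterion 7; must be true).
- C: the person is not contraindicated to, and in the investigator's view is a candidate for, at least one of the same four (criterion 41; must be false, because meeting it excludes).

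Literal eligibility on these two criteria is therefore A and not-C.

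**The four cases**

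- A and C: meets criterion 7, excluded by criterion 41.
- A and not-C: meets criterion 7, not excluded by criterion 41. This is the only eligible case.
- not-A and C: fails criterion 7 and is excluded by criterion 41.
- not-A and not-C: fails criterion 7.

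The eligible case is small but not empty, because criterion 7 asks for agreement and not for suitability. It consists of people who agree to use an antiseptic although they are unsuited to all four.

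**Can the sentence be read another way?** One could take the contraindication clause to mean that none of the four is contraindicated. That does not help. The second clause, on being a candidate for use, is affirmative, so suitable people are still excluded. The sentence is complete in the text, with no sign of redaction or of damage in reading the PDF. The list of changes in the protocol amendment covers criteria 12, 16 and 35, and does not mention 41.

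**Size under the literal reading only**

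Inputs: about 100 screened and about 63 randomized (Protocol Sections 1.1 and 9.2), a planned yield of 63/100 = 63%. Let q be the share of screened people unsuited to all four antiseptics. The documents do not give q, so the values below are assumptions. They also take the most favorable case, in which all such people agree to use an antiseptic and meet every other criterion.

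Most who could pass = 100 × q. Least screening needed for 63 randomized = 63 / q.

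| Assumed q | Most eligible of 100 | Least screened for 63 |
|---|---|---|
| 0.1% | 0.1 | 63 / 0.001 = 63,000 |
| 1% | 1 | 63 / 0.01 = 6,300 |
| 5% | 5 | 63 / 0.05 = 1,260 |

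To reach the planned yield under the literal text, q would have to be at least 63%. The recruitment plan therefore cannot have been built on the literal wording.

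**Does it reach the analysis?** The mITT population needs randomization and at least one dose. The per-protocol set in SAP Section 6.3.1 depends on missed doses. Neither refers to eligibility criteria, so the wording alone moves nobody into or out of an analysis set.

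**The case against.** The strongest reply is that this is a drafting slip with an obvious meaning. The synopsis, criterion 7 and Section 6.5.2 all require antiseptic use, and the last two name the same products as criterion 41. The amendment's rationale says that discontinuation had been higher than expected, so participants had already been enrolled and treated. Criterion 41 is not among the listed changes, which suggests that its wording was already in force, although the previous version of the protocol is not available to confirm this. If it was in force, sites were not applying it literally. Criteria 32 (drug allergies) and 44 (unsuitable in the investigator's or sponsor's opinion) also give some protection against enrolling people who should not use the antiseptics.

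Most of this stands, and it limits the point. A reader might be tempted by four stronger conclusions that the documents do not support:

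- *That nobody could be eligible, or that every randomized participant is ineligible.* The literal set is very small, not empty.
- *That all of about 63 participants are important protocol deviations.* SAP Section 6.11 names incorrect enrollment only as a potential example and leaves importance to later assessment.
- *That Section 7.2.1 would force participants off treatment.* It applies only once someone identifies a participant as ineligible, and it contains a route to continue.
- *That reading criterion 41 as evidently intended creates a safety gap.* It is the reverse: the intended reading keeps out people unsuited to the antiseptics, and the literal one lets them in.

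There is also no evidence that sites differed in how they read it. What the reply does not remove is the contradiction. Under a protocol without waivers, correct enrollment depends on every site disregarding a written exclusion.

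**Conclusion.** The contradiction is real and nothing in the documents resolves it. As written, criterion 41 excludes the people whom criterion 7, the synopsis and Section 6.5.2 require, and nearly every randomized participant would technically meet it. The table's figures rest on the literal reading and on assumed shares. They show that the wording cannot be what was planned, and they do not estimate lost recruitment.

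The practical effect is probably small, given the evident intent and the enrollment already achieved. The documents do not show how sites applied the criterion. Power, alpha and the primary analysis are unaffected. What remains is an eligibility rule that gives the wrong result if followed, and that leaves the eligibility of almost any participant open to dispute at audit or deviation review.

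**What to change.** Reconcile criterion 41 with criterion 7 and Section 6.5.2 in the next amendment. If the intent is that participants must be able to use one of the antiseptics, either restate criterion 41 as the negation of its present text or move it to the inclusion list in Section 5.1. It would also help for the deviation review under SAP Section 6.11 to record how criterion 41 was read for participants enrolled before the correction, so that they are handled consistently.

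The cost is one corrected line. Sites that already read the criterion in line with criterion 7 change nothing, and no analysis, sample size or visit schedule is touched.
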